A randomized trial evaluating single fraction stereotactic versus standard multi-fraction radiotherapy for patients diagnosed with bone metastases for effective palliation of symptoms.

1. OBJECTIVES:

- a. Primary objective (phase II): evaluate single fraction stereotactic regimen for pain response in terms of time to failure, defined as the first occurrence of any of the following events:
 - i. worsening in pain score by at least 2 categories by MDASI survey,
- b. Primary objective (phase III): to evaluate the pain response at 3 months in terms of pain response by a decrease in 2 categories by MDASI survey and narcotics use as defined by international pain consensus criteria.
- c. Secondary objective: report outcomes
 - i. Compare narcotics/opioid use compared to baseline, $\geq 50\%$ increase in dose of opioid/narcotic medication,
 - ii. re-irradiation,
 - iii. radiographic disease progression or development of pathologic fracture from disease progression
 - iv. Prospectively report pain, quality of life, and symptoms using MDASI assessment tool to measure pain response
 - v. Report acute (skin, fatigue, flare reaction) and long term (sclerosis, bone ossification, bone fracture rate) toxicity associated with treatment.
 - vi. Report local control and overall survival
 - vii. Report rate of salvage surgery

2. BACKGROUND:

- a. Radiation therapy is commonly utilized to effectively palliate symptomatic bone metastases, 50%-80% of patients experience improvement in the pain and 20%-50% report complete pain relief (1, 2). However, the optimal fractionation scheme to produce durable pain relief is still being studied. Historically, clinical trials have compared efficacy of varying dose-fractionation in alleviating symptoms. Ratanatharathorn et al. concluded in their analysis that higher dose fractionated treatments produced better pain outcomes compared to lower-dose regimens (3, Ratanatharathorn). Contrary to this, McQuay et al. in their summary determined no difference in efficacy between different fractionation or dose response in the total dose delivered for painful bone metastases (4, McQuay). In the meta-analysis performed by Wu et al (5, Wu) the authors compared pain relief among various dose-fractionation schedules of localized radiotherapy (RT) in the treatment of painful bone metastases. They concluded among the randomized trials, there was no significant difference in overall pain

relief or dose response relationship between single and multi-fraction palliative RT for bone metastases.

In the last two decades, multiple randomized trials have compared the efficacy of various dose-fractionation in achieving durable pain relief in patients diagnosed with bone metastases. A randomized trial, RTOG 9714 investigated whether 8 Gy delivered in a single fraction provided pain and narcotic relief equivalent to the standard 30 Gy in 10 fractions. The study demonstrated both regimens were equivalent in terms of pain and narcotic relief, and well tolerated with few adverse effects. The shorter 8 Gy arm had a higher re-treatment rate but with less acute toxicity than the longer 30 Gy arm (6, Hartsell). However, the Trans-Tasman Radiation Oncology Group (TROG 96.05) was a randomized trial which demonstrated 8 Gy in a single fraction was not as effective as 20 Gy in 5 fractions; the overall response rate and time to treatment failure were inferior (7, Roos). The re-treatment rate has been reported to be higher in patients treated by single fraction radiotherapy; this could be due to the decrease in durability of pain response related to the lower dose equivalent (8, Sze).

A single delivery of higher dose of radiation treatment can be advantageous in regards to patient convenience and cost effectiveness as long as it can provide durable pain control. The optimal single fraction dose required to achieve pain control is still unknown and not determined from current clinical trials. Gaze et al demonstrated an overall pain response rate of 84% and complete pain response rate of 34% with delivery of a single fraction of 10 Gy (9, Gaze) for patients with osseous metastases. Higher doses of 12 Gy and 15 Gy have demonstrated a dose response of increased overall pain response of 86% and complete pain response in 57% of patients (10, Kagei). Radiosurgery doses of ≥ 16 Gy has been shown to increase the probability of pain relief for patients with spine metastases by multiple institutions such as Henry Ford and University of Pittsburgh (11, 12, Ryu, Gerzten). Researchers at M.D. Anderson have demonstrated the use of single fraction SBRT with doses of 16-24 Gy for spinal metastases was safe and allowed patients to achieve durable local control (88% at 18 months) with few toxicities (13, Garg).

Multiple prospective randomized trials have investigated the efficacy of shorter versus longer fractionated radiation therapy courses for the treatment of painful bone metastases with conflicting results. Few studies prospectively address the relief of neuropathic pain, re-irradiation rates, fracture rates and prospective quality of life endpoints. In this study, we propose to deliver a dose escalated single fraction (12 Gy or 16 Gy) regimen compared to the standard 20 Gy in 5 fractions to report the safest optimal hypofractionated regimen in providing durable symptomatic relief.

3. SCIENTIFIC RATIONALE:

- a. This study aims to prospectively evaluate the optimal radiation therapy dose to provide durable pain relief, assess patients' quality of life, narcotics use after radiation therapy, outcome, and toxicity. The goal of this prospective randomized trial is to radiate patients with mechanically stable, painful bone metastases effectively to provide quick palliation of pain. The hypothesis is rapid delivery of dose escalated hypofractionated radiotherapy for bone metastases effectively improves pain and results in durable pain control.

4. PATIENT ELIGIBILITY

a. INCLUSION:

- i. Patients with a pathologic diagnosis of malignancy
- ii. Patients with any radiographic evidence of bone metastases, including plain x-ray, bone scan, CT scan, MRI, or PET scan
- iii. Patients with pain or dysaesthesia
- iv. Patients with a life expectancy of more than 3 months
- v. Patients able to complete pain assessment and quality of life surveys
- vi. Patients with multiple osseous sites are eligible; however should not treat more than 3 separate radiation treatment fields concurrently.
- vii. Patients with surgery for osseous metastases allowed.

b. EXCLUSION:

- i. Patients with prior radiation therapy to the treatment site
- ii. Patients with a current, untreated spinal cord compression
- iii. Patients with a radiographic or pathologic fracture to the treatment site
- iv. Patients with painful metastases to hands and feet that need to be radiated on protocol
- v. Patients previously treated with radioactive isotope (e.g. Sr89) within 30 days of randomization

5. PRE-TREATMENT EVALUATION:

- a. The workup will include physical examination, radiographic evidence of metastases with either x-ray, bone scan, CT scan or MRI, and pathologic confirmation of malignancy per MDACC standard of care.
- b. All eligible patients will be enrolled after completion of the eligibility checklist.
- c. Use of pain medications (narcotic/opioids/NSAIDs) will be evaluated.

6. TREATMENT PLAN:

- a. Patients will be randomized to receive radiation therapy to:
 - i. Arm 1: the standard hypofractionated regimen of 3 Gy x 10 fractions
 - ii. Arm 2: 12 Gy x 1 fraction or 16 Gy x 1 fractions adaptively depending on the size of the metastases or gross tumor volume (GTV).
- b. Patients will undergo CT simulation and either 2-D or 3-D treatment planning for radiation therapy.

- c. Patients can be treated with 2-D, 3-D, or intensity modulated radiation therapy (IMRT)
 - d. Patients will be treated with on board imaging (OBI) using KV, MV x-rays, cone beam CT or CT on rails per standard of care.
 - e. Patients will be treated with 4-20 MV photon beam, 5-20 MeV electron beam, or 200 MeV-300 MeV proton beam.
 - f. More than 1 osseous site may be included into one radiation treatment field.
7. EVALUATION DURING STUDY:
- a. All patients will be evaluated by the radiation oncologist during radiation treatment
 - b. If surgical intervention is necessary, the patients will be evaluated by the treating surgeon
 - c. After start of treatment, all patients will be followed by phone calls within 7-14 days, and at + 1 month (+/- 1 week) and then with clinic visits at months 3, 6, 9, 12 (+/- 4 weeks for each visit) and every 3 to 6 month intervals thereafter (until death) by either the radiation oncology or orthopedic team to evaluate toxicity. The validated surveys (MDASI) will be completed at baseline prior to radiation and at each follow up interval/appointments. The patient medical record number will be placed on the survey before it is given to the patient for completion. The surveys may be filled out in person or by mail.
 - d. Patients will report their symptom measures with validated quality of life instrument MDASI index. The M.D. Anderson Symptom Inventory (MDASI) is a multi-symptom patient reported outcome measure evaluating 13 core symptom items interfering with patients' daily life (Appendix B).
 - e. We will also prospectively report the narcotics/NSAIDs utilization and outcome at each follow-up interval after radiation therapy.
8. EVALUATION OF TOXICITY:
- a. During radiotherapy, the patient will be examined weekly and acute reactions recorded.
 - b. Toxicity occurring after 3 months of radiation therapy; these will be evaluated and documented using NCI CTCAE version 4.03 (Appendix A).
9. CRITERIA FOR RESPONSE:
- a. The response to treatment will be determined by both radiographic scans and symptoms reported.
 - b. Complete pain relief is defined as average pain score of 0 for two consecutive analysis periods.
 - c. The time to maximal relief of pain is defined from the first day of irradiation until the lowest pain score after radiation therapy.

- d. Treatment failure is defined as worsening of pain by at least two categories, >50% increase in dose of opioid/narcotic medications, re-irradiation for pain or disease progression, progression or development of pathologic fracture from disease progression.
 - e. Any patient with progressive pain in the radiated area will have work up which include radiographic scans to evaluate for bone stability and pathologic fracture per standard of care.
10. RE-TREATMENT:
- a. Response and pain relief from radiation therapy may take several weeks; therefore patients should not be re-irradiated for at least 4 weeks after completion of radiation. Dose and fractionation are left to the discretion of the treating radiation oncologist.
 - b. Surgical intervention for treatment failures, bone instability, or fractures will be reported.

11. STATISTICAL CONSIDERATIONS:

This is a phase II/III non-inferiority trial following the design suggestions of Korn et al. (14, Korn). The primary outcome for phase II part is treatment failure at 1 month, where treatment failure is as defined in section 1.0. We assume that time to treatment failure follows an exponential distribution for each treatment arm (standard radiation, hypofractionated radiation). We also assume that the standard radiation arm will have 25% of patients with treatment failure at 3 months, based on the study by the Bone Pain Trial Working Party (15, BPTWP). A hazard ratio of 1.5 implies that the hypofractionated radiation arm will have 35% of patients with treatment failure at 3 months. The primary outcome for phase III part is pain response rate at 3 months post randomization. We expect to enroll 10 patients per month.

Randomization

Patients will be randomized to standard or single fraction stereotactic radiation therapy using CORE. Randomization will be stratified by tumor size (≤ 4 cm vs. > 4 cm), site of bony mets (extremities, pelvis, abdomen, head/neck, chest), and 1 vs >1 site irradiated. We expect approximately 40% of patients will have bony mets in the extremities and approximately 35% will have bony mets in the pelvis. We expect the distribution of patients enrolling will approximately be 40% lung malignancy, 25% genitourinary malignancy, 15% breast malignancy, 10% multiple myeloma and 10% other malignancy. We will have a total of 14 stratification levels.

Phase II

We will test the following hypothesis:

$$H_0: \rho = 1.5 \quad \text{vs.} \quad H_1: \rho = 1.0,$$

where ρ is the hazard ratio (hypofractionated/standard) for time to treatment failure, as defined in section 1.0. A sample size of 150 patients (75 randomized to each treatment arm) will yield 90% power with a 1-sided significance level of 0.20 to reject the null hypothesis (H_0) and conclude that hypofractionated treatment is not inferior to standard treatment in terms of time to treatment failure. We use a 1-sided significance level of 0.20 as recommended by Rubinstein et al. (16, Rubinstein) for phase II screening trials. This sample size will yield 110 events (i.e., treatment failures). It will take 15 months to enroll all the patients, and the maximum study duration is expected to be 22 months to observe the 110 events. The final analysis for phase II will be performed once we've observed 110 events, and we will suspend accrual while we wait for these events to occur. We will continue to phase III only if we reject H_0 at the 0.20 significance level.

Phase III

The patients enrolled in the phase III part of the study will be included in the phase III part of the study. In the Phase II trial, we have already enrolled and randomized 160 patients, therefore we are requesting to enroll another additional 50 patients to reach a total of 210 patients. We will enroll another 50 patients in total of 210 patients (105 randomized to each treatment arm), after the rejection of the H_0 in the phase II part of the trial. The primary objective is to evaluate the pain response at 3 months by international pain consensus criteria after the additional 50 patients have been accrued, we will follow all patients for at least 3 months to assess the pain response. Assuming a 20% of the 3-month pain response rate for patients on MFRT arm, the 210 patients will ensure an 80% power to detect a 16% improvement in response rate (36%) with SBRT using a 1-sided 5% level test.

Pain response at 3 months is defined as reduction in pain score reported by MDASI at 2 points below baseline also taking into account narcotics use, as defined by International Pain Response Criteria.

This sample size calculation was performed using East 6 (Copyright © 2010, Cytel Inc., Cambridge, MA).

Toxicity Monitoring (phase II and phase III)

We will monitor the rate of radiation induced toxicity (skin dermatitis grade ≥ 4 , gastrointestinal (GI) grade ≥ 3 , genitourinary (GU) grade ≥ 3) by 12 months after the start of radiation therapy for the hypofractionated radiation therapy arm. We will enroll at least 25 patients and at most 105 patients on this treatment arm, and we will use the methods of Thall et al. (17, Thall et al.) to monitor the radiation induced toxicity rate.

We will stop enrolling patients on the hypofractionated radiation therapy arm if we have reason to believe that the rate of radiation induced toxicity for this arm is more than 10%.

We will actually monitor the time to radiation induced toxicity, because these toxicities may occur at any time from the start of radiation therapy. We will use the Clinical Trial Conduct website (<https://biostatistics.mdanderson.org/ClinicalTrialConduct>) to monitor the toxicity stopping rule. This website is built and maintained by the Department of Biostatistics. The research staff will be trained by the study statistician in the use of the website to monitor the stopping rules, with an emphasis on the importance of updating toxicity outcomes and follow-up dates.

To obtain the operating characteristics for the stopping rule we simulated the trial 1000 times for various scenarios described in the table below. We assumed that patients are enrolled at the rate of 5 per month on the hypofractionated radiation therapy arm, that we would follow patients for 12 months, and that we will evaluate the stopping rule continually. The table below summarizes the operating characteristics of this stopping rule.

Operating Characteristics for the Toxicity Monitoring Rule						
Median time to radiation induced toxicity (months)	12-Month Toxicity Rate	Pr(Stop Early)	Sample Size			Avg Trial Duration (Months)
			P ₂₅	Mean	P ₇₅	
120	0.07	< 0.001	105	105	105	33.2
60	0.13	0.113	105	103	105	32.8
40	0.19	0.667	77	89	105	30.1
30	0.24	0.949	60	73	85	26.9

At any point in the trial time to radiation induced toxicity can be calculated for each patient, with the time interval regarded as censored at the date of last follow-up if toxicity has not been observed for a patient. We will apply a Bayesian method for updating prior information with time to toxicity data observed to that time. We assume that the time to toxicity for each patient is exponentially distributed with a median of λ_S months for the standard treatment and a median of λ_E for the experimental treatment. Given the historical data we assume λ_S follows an inverse gamma distribution with mean 78.95 months and a standard deviation of 0.15 months. The middle 95% of this distribution is between 78.66 and 79.24 months. These parameters correspond to a 12-month toxicity rate between 9.064% and 10.035%. We assume λ_E follows an inverse gamma distribution with a mean of 78.95 months and a standard deviation of 15.0 months. The middle 95% of this distribution is between 54.87 and 113.32 months. These parameters correspond to a 12-month toxicity rate between 7.077% and 14.066%.

Since the goal of the study is to achieve a toxicity rate of less than 10% at 12 months, the trial will be stopped early if, based on the available data, $\Pr(\lambda_E < \lambda_S \mid \text{data from the trial}) > 0.90$. This rule was chosen to achieve an approximately 0.10 early stopping probability if the true toxicity rate is 10%.

Final Analysis

We will use descriptive statistics to summarize the demographic and clinical characteristics of patients by treatment arm.

We will use the methods of Gooley et al. (18, Gooley) to estimate the cumulative incidence of treatment failure for each treatment arm with death as a competing event, and we will estimate the percent of patients without treatment failure at 3, 6, and 12 months for each treatment arm with a 90% confidence interval.

We will use the methods of Fine and Gray (19, Fine and Gray) to model time to treatment failure with death as a competing event and test the hypotheses stated above for phase II and for phase III. We will also estimate the hazard ratio for treatment with a 90% confidence interval.

For the 3 month pain response rate, the Cochran-Mantel-Haenszel test stratified by stratification factors at randomization will be used to test the difference between 2 treatment arms. Chi-squared test without adjusting for the stratification factors will also be performed as a secondary analysis.

We will use descriptive statistics and boxplots to summarize the score from the MDASI instrument at each assessment time. We will similarly summarize changes in scores for these instruments over time. We will use mixed effects regression methods with repeated measures and patient as a random effect to model instrument scores over time to test for treatment differences.

We will use the product limit estimator of Kaplan and Meier (20, Kaplan and Meier) to estimate overall survival and disease-free survival stratified by treatment arm. We will use Cox proportional hazards regression to model OS and DFS as a function of treatment arm, and we will estimate the hazard ratio for treatment with a 90 % confidence interval (21, Cox).

We will use descriptive statistics to summarize narcotics use and acute and long-term adverse events for each treatment arm.

We will use Fisher's exact test to compare treatment arms with respect to the rates of re-irradiation and salvage surgery.

12. Database:

Study data will be collected and managed using REDCap (Research Electronic Data Capture) electronic data capture tools hosted at MD Anderson. [ref 22] REDCap (www.project-redcap.org) is a secure, web-based application with controlled access designed to support data capture for research studies, providing: 1) an intuitive interface for validated data entry; 2) audit trails for tracking data manipulation and export procedures; 3) automated export procedures for seamless downloads to common statistical packages; and 4) procedures for importing data from external sources. REDCap (<https://redcap.mdanderson.org>) is hosted on a secure server by MD Anderson Cancer Center's Department of Research Information Systems & Technology Services. REDCap has undergone a Governance Risk & Compliance Assessment (05/14/14) by MD Anderson's Information Security Office and found to be compliant with HIPAA, Texas Administrative Codes 202-203, University of Texas Policy 165, federal regulations outlined in 21CFR Part 11, and UTMDACC Institutional Policy #ADM0335.

13. REFERENCES:

1. Bates T. A review of local radiotherapy in the treatment of bone metastases and cord compression. *Int J Radiat Oncol Biol Phys* 1992; 23:217-221
2. Maher EJ. The use of palliative radiotherapy in the management of breast cancer. *Eur J Cancer* 1992; 28:706-710.

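### Eligibility sets no minimum pain score, so patients with baseline pain 0–1 cannot meet the score part of phase III response, and the primary test ignores baseline pain

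*Combined protocol and SAP*

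**What the plan says.** - **Eligibility.** Section 4.a.iii requires "Patients with pain or dysaesthesia". No minimum pain score appears in the inclusion criteria, the exclusion criteria or the pre-treatment evaluation (section 5). A score of 1, or a score of 0 with dysaesthesia alone, is admissible as written.
- **Phase III endpoint.** Section 11 (Phase III) states "Pain response at 3 months is defined as reduction in pain score reported by MDASI at 2 points below baseline also taking into account narcotics", and refers to the international criteria. Section 1.b puts it as "pain response by a decrease in 2 categories by MDASI survey and narcotics use as defined by international pain consensus criteria". The criteria themselves are not reproduced, and nothing says how patients starting at 0 or 1 are classed or whether they stay in the denominator.
- **Complete relief.** Section 9.b states "Complete pain relief is defined as average pain score of 0 for two consecutive analysis periods". It refers neither to baseline nor to narcotics.
- **Sample size.** Section 11 plans 105 patients per arm, "Assuming a 20% of the 3-month pain response rate for patients on MFRT arm", and claims "80% power to detect a 16% improvement in response rate (36%) with SBRT using a 1-sided 5% level test".
- **Analysis.** The primary test is a Cochran-Mantel-Haenszel test over the randomisation factors: tumour size, bony site, and one versus several irradiated sites. An unadjusted chi-squared test is secondary. Baseline pain is in neither.
- **Data.** MDASI is completed before radiation (section 7.c and Table A).

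**The concern.** The endpoint is a change score with a floor. Baseline pain decides whether the required change is possible at all, yet it is absent from eligibility, from stratification and from the primary test. Patients at the floor add non-responses to both arms on the score component whatever the treatment does. The estimated difference then understates the effect among patients who could respond, and the test carries patients who supply no information about that component. The rule for these patients is also unwritten. Unless it is settled beforehand, the denominator could be chosen after the results are known.

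**Working it through.** **1. Is the 2-point fall attainable?** Section 9.b treats 0 as complete relief, so 0 is taken as the lowest score. The largest possible fall is 1 − 0 = 1 point from baseline 1, and 0 points from baseline 0. Both are below 2.

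**2. The plan's own power.** Inputs from section 11: n = 105 per arm, p1 = 0.20, p2 = 0.36, 1-sided 5% (z = 1.645). Formula: power = Φ[(p2 − p1 − z·s0)/s1], where s0 = √(2p̄(1 − p̄)/n), s1 = √((p1(1 − p1) + p2(1 − p2))/n) and p̄ is the mean of p1 and p2.

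With p̄ = 0.28, s0 = 0.06197 and s1 = 0.06098: (0.16 − 1.645 × 0.06197)/0.06098 = 0.952, so power = 0.830. Exact enumeration with Fisher's test gives 0.793. The stated 80% is reproduced: close to the Fisher figure, and slightly conservative for an uncorrected test.

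**3. Floor patients, reading A: 20% and 36% apply only to patients able to fall 2 points.** Let f be the share at baseline 0–1 in each arm (an assumption; no value is given), all counted as non-responders. The rates become 0.20(1 − f) and 0.36(1 − f). For f = 10% they are 0.180 and 0.324, p̄ = 0.252, s0 = 0.05992, s1 = 0.05909, and (0.144 − 1.645 × 0.05992)/0.05909 = 0.769, so power = 0.779.

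**4. Reading B: 20% and 36% are whole-arm rates that already include floor patients.** All-randomised power stays at 0.830 for any f. Among patients with baseline of 2 or more, the rates are then 0.20/(1 − f) and 0.36/(1 − f).

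**5. Results.** The last two columns test only patients with baseline of 2 or more, at n = 105(1 − f) per arm.

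| f (assumed) | Rates, all randomised, A | Difference | Power, all randomised, A | Power, baseline ≥2, A | Power, baseline ≥2, B |
|---|---|---|---|---|---|
| 0% | 20.0% / 36.0% | 16.0 points | 0.830 | 0.830 | 0.830 |
| 5% | 19.0% / 34.2% | 15.2 points | 0.805 | 0.812 | 0.837 |
| 10% | 18.0% / 32.4% | 14.4 points | 0.779 | 0.793 | 0.845 |
| 20% | 16.0% / 28.8% | 12.8 points | 0.721 | 0.750 | 0.864 |

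Under A, all-randomised power is 0.800 at f = 6%, so it falls below the planned level just above that share. The total N for 80% power by the same formula is 194 at f = 0, 208 at 5%, 224 at 10% and 262 at 20%, against 210 planned.

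**6. Why stratifying does the same work as restricting.** If nobody at baseline 0–1 responds, a stratum made of those patients has no responders. It then adds nothing to the observed-minus-expected sum or to the variance in the Cochran-Mantel-Haenszel statistic. Splitting on baseline 0–1 versus 2 or more therefore recovers the gain in the last two columns, apart from the other strata, without removing anyone from the analysis set.

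**7. Section 9.b against section 11.** A patient at baseline 1 who scores 0 at two assessments in a row has complete relief under 9.b but has fallen only 1 point. A patient who starts and stays at 0 also meets 9.b, with no improvement.

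**The case against.** The strongest objection is that the endpoint is not the score alone. Narcotics use enters under international criteria that are not printed, so a reader who infers that low-baseline patients can never be responders goes further than the documents allow. That stands: only the score component is shown to be out of reach, and the dilution figures assume that the narcotics component does not rescue these patients.

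Second, the size is conditional. Section 3 describes the target population as having painful metastases, so the share may be small; at 5% power is still 0.805. Section 11 attaches the 20% to patients on the multi-fraction arm, which can be read as a whole-arm rate, and then planned power does not move. Both stand.

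Third, a reader might infer that sections 9.b and 11 contradict each other outright. They do not. Section 9.b defines complete pain relief, not response; it needs zeros over successive assessments rather than a single fall to 0; and no analysis in section 11 uses it. Two measures may class one patient differently. What remains is a need to say how they relate.

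Fourth, it is tempting to make baseline of 2 or more the primary set. With 160 patients already randomised, that changes the target population late, drops dysaesthesia patients whom section 4 admits, and might discard responders on the narcotics component. The all-randomised comparison is valid because randomisation balances floor patients on average.

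The objection does not remove the unwritten rule or the unused baseline score. Under either reading of the planning rates, testing where response is possible gives more power.

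**Conclusion.** The point holds in limited form. As written, patients with baseline pain 0–1 may enrol, cannot meet the score component of phase III response, and are not accounted for in the primary test. The consequence is dilution and lost precision, not bias. Under reading A, power falls from 0.83 to 0.805, 0.779 or 0.721 at assumed shares of 5, 10 or 20%; under reading B the planned power is unaffected. Using baseline pain recovers a modest amount: 1.4 points at a 10% share and 2.9 at 20% under A, and 1.5 and 3.4 under B. Under A it does not restore 80% at either of those shares. These figures rest on the pooled normal approximation, equal shares in the two arms, and no response through narcotics among floor patients. This is a low-cost improvement and does not invalidate the design.

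**What to change.** 1. Keep all randomised patients as the primary analysis set.
2. Pre-specify a 3-month response analysis adjusted for baseline MDASI pain, for example a logistic model with treatment, the randomisation factors and baseline pain as a continuous term, or a Cochran-Mantel-Haenszel test further split at baseline 0–1 versus 2 or more. The model is safer against sparse strata: the existing factors fully crossed give 2 × 5 × 2 = 20 cells for 210 patients. The precision gain reaches the primary p-value only if this analysis is named as the primary test, so fix its status before comparative phase III results are seen.
3. Add a sensitivity analysis limited to baseline pain of 2 or more, and report the number at 0–1 by arm.
4. Print the response rule in full, including the narcotics component and the classification of patients starting at 0 or 1.
5. State that complete pain relief in section 9.b is a separate descriptive measure and how it relates to the section 11 definition.

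The cost is SAP wording and a little more analysis; the baseline score is already collected. The sensitivity set is smaller. An eligibility change would reach only the last 50 patients, so an analysis rule is the practical route.

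### In-person examinations for acute reactions recur only in the multi-fraction arm, so the by-arm acute toxicity summary risks unequal ascertainment that would tend to favour the single fraction

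*Combined protocol and SAP*

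**What the plan says.** Section 8.a links the recording of acute reactions to time on treatment: "During radiotherapy, the patient will be examined weekly and acute reactions recorded". Section 6.a sets very different treatment times: "Arm 1: the standard hypofractionated regimen of 3 Gy x 10 fractions" against "12 Gy x 1 fraction or 16 Gy x 1 fractions".

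Two provisions cover both arms. Section 7.a states: "All patients will be evaluated by the radiation oncologist during radiation treatment". Section 7.c states that "all patients will be followed by phone calls within 7-14 days, and at + 1 month", counted from the start of treatment, with clinic visits from month 3 (+/- 4 weeks); it gives toxicity evaluation as the purpose of this follow-up.

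Table A (section 14) is printed twice. The second version marks a toxicity/AE assessment at both early calls. The first marks none between the pre-treatment row and month 3.

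Objective 1.c.v lists skin, fatigue and flare reaction as the acute toxicities to report. The Final Analysis part of section 11 says: "We will use descriptive statistics to summarize narcotics use and acute and long-term adverse events for each treatment arm".

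**The concern.** How often a patient is examined in person for acute reactions depends on the randomized arm. An Arm 1 patient is examined again while reactions may be developing. An Arm 2 patient's only in-person evaluation falls on the treatment day, before most reactions could appear, and the next scheduled clinic visit is month 3. The two calls in between reach both arms, but skin cannot be inspected by telephone. Section 8 names a grading scale (CTCAE 4.03) only for toxicity after 3 months, so it does nothing to align examination findings with telephone findings.

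If the arms had the same true rate of acute reactions, more would tend to be recorded in Arm 1. Readers will set the two columns side by side: the Background cites lower acute toxicity as a feature of a shorter regimen, and the study aims to report the safest effective schedule. The plan has no rule that separates findings from the extra examinations from findings at shared contacts.

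**Working it through.** The plan states no acute toxicity rate and no sample size or power for it, so there is no figure to reproduce. The check is a count of contacts, followed by an illustration.

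**1. Course length.** Ten fractions at five per week (an assumption) span at least 5 + 2 + 5 = 12 days, or about two weekly examinations. One fraction takes one day, so no weekly examination recurs. The end of the Background names a five-fraction standard arm, which must be reconciled with section 6.a. Five weekday fractions would give about one examination, and the direction would be the same.

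**2. Toxicity contacts from start of treatment through month 3.**

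| Basis | Arm 1 | Arm 2 |
|---|---|---|
| Section 7.c and second Table A | 2 examinations + 2 calls + 1 visit = 5 | 1 treatment-day evaluation + 2 calls + 1 visit = 4 |
| First Table A (no toxicity item at calls) | 2 examinations + 1 visit = 3 | 1 treatment-day evaluation + 1 visit = 2 |

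Under the first Table A, Arm 2 has no scheduled toxicity assessment between the treatment day and month 3. Arm 1's second examination, at about day 12, falls close to the 7-14 day call. Arm 1 therefore gains roughly one extra time point, plus the in-person mode.

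**3. Clock.** Section 7.c and the second Table A count from the start of treatment. The first Table A puts the first call 7-10 days after radiotherapy. If that means after completion, the call falls at about day 12 + 7 to 12 + 10 = 19 to 22 in Arm 1, and day 1 + 7 to 1 + 10 = 8 to 11 in Arm 2.

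**4. Illustration.** All rates here are assumed; none is in the documents. The true acute rate is 30% in both arms. Each examination detects a reaction with probability e (0.5 to 0.8) and each call with probability c, independently. The month 3 visit is left out, and Arm 2's treatment-day evaluation is taken as too early to detect anything.

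Recorded rate = 0.30 x [1 - (1 - e)^k x (1 - c)^2], with k = 2 in Arm 1 and k = 0 in Arm 2.

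For example, with e = 0.5 and c = 0.3, Arm 1 gives 0.30 x (1 - 0.25 x 0.49) = 26.3% and Arm 2 gives 0.30 x (1 - 0.49) = 15.3%.

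| c | Arm 1 | Arm 2 | Gap, points | Gap if k = 1 |
|---|---|---|---|---|
| 0 | 22.5-28.8% | 0% | 22.5-28.8 | 15.0-24.0 |
| 0.3 | 26.3-29.4% | 15.3% | 11.0-14.1 | 7.3-11.8 |
| 0.6 | 28.8-29.8% | 25.2% | 3.6-4.6 | 2.4-3.8 |
| 0.8 | 29.7-30.0% | 28.8% | 0.9-1.2 | 0.6-1.0 |

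The gap has the same sign throughout. Its size depends almost entirely on how well the calls work. The row c = 0 corresponds to calls without a toxicity item, as in the first Table A.

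**5. Shared contacts only.** With k = 0 in both arms, both record 0.30 x [1 - (1 - c)^2], for example 15.3% at c = 0.3. The spurious gap disappears in this model, at the price of fewer Arm 1 reactions counted in the comparison.

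**The case against.** The strongest reply is that the weekly examinations are not the only source of acute data. Section 7.a covers all patients. Section 7.c puts both arms on one clock from the start of treatment, with toxicity evaluation as its purpose. The second Table A, whose timing matches section 7.c, marks toxicity at both calls. MDASI is also completed at baseline and at every follow-up in both arms, which gives pain flare a common measure. No test is planned: objective 1.c.v says to report acute toxicity, while other outcomes are explicitly to be compared.

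Most of this stands. It rules out three stronger conclusions that a reader might infer:

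- **That the summary is known to be biased, by a stated amount.** The documents give no detection rates, and good telephone capture would leave a gap of about 1 point.
- **That Arm 1 has twice the surveillance.** The nominal count is 5 against 4, and one Arm 1 examination nearly coincides with a call.
- **That the trial's main conclusions are threatened.** The primary endpoints rest on treatment failure and pain response. The toxicity stopping rule concerns the single-fraction arm alone, so a difference in ascertainment between the arms does not enter it.

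The reply does not restore equal in-person examination. Section 7.a gives Arm 2 only a treatment-day look, and a call cannot show skin. It also relies on the second Table A, while the first is still in the document with nothing to say which governs.

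**Conclusion.** The point holds as a risk of differential ascertainment in one secondary, descriptive output. Repeated in-person examinations for acute reactions occur only in the multi-fraction arm, about two of them if fractions are given on weekdays. Any resulting difference would tend to under-record reactions in the single-fraction arm, most plausibly for skin. The range of about 1 to 29 points comes from assumed inputs and shows only that the size is undetermined; the upper end requires calls that capture no toxicity. The disagreement between the two versions of Table A is a separate, definite defect, and following the first would make the imbalance worse. This is a cheap improvement, with no bearing on the primary analyses.

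**What to change.** 1. Reconcile Table A with section 7.c, so that toxicity is recorded at both early calls in both arms.
2. State in section 8 and in the Final Analysis that the by-arm acute toxicity comparison uses only contacts common to both arms: 7-14 days, 1 month and 3 months from the start of treatment. Ask the same skin, fatigue and flare items at each, over the same window (since the start of radiotherapy), whether or not a weekly examination took place. A window running from the last contact would be shorter in Arm 1 and could reverse the imbalance.
3. Report weekly on-treatment findings in a separate table that is not used to compare the arms, and say in the report that in-person surveillance differed by arm.

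The cost is a few sentences and one corrected table, with no new visits. There are four limits:

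- Some reactions seen only at Arm 1 examinations leave the comparison, although they are still reported.
- Calls remain weak for skin.
- Arm 1 may still be on treatment at the 7-14 day call, so the 1-month contact matters most.
- With 160 of 210 patients already randomized, standardised items help mainly the remaining 50. The analysis rule can cover earlier patients whose calls recorded toxicity.
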